Treatment-related AEs were seen in 39/44 patients (89%), including 16/21 (76.2%) in N3 + I1 and 23/23 (100%) in N1 + I3. Across the N3 + I1 and N1 + I3 arms, the most common (\geq 20%) treatment related AEs of any grade were fatigue (61%), diarrhea (32%), nausea (30%), rash (27%), pruritis (25%), ALT increased (23%), AST increased (20%), hypothyroidism (20%), and lipase increased (20%). Grade 3-4 related AEs occurred in 19 patients (29%), including 6/21 (29%) at N3 + I1 and 14/23 (61%) at N1 + I3. The most common (\geq 5%) drug-related grade 3-4 events were lipase increased (21%), ALT increased (14%), AST increased (7%), diarrhea (9%), fatigue (5%), amylase increased (5%), colitis (5%), lymphocyte count decreased (5%). No grade 3-4 pneumonitis was seen. No treatment-related deaths were reported.

Treatment-related AEs (including Grade 3-4), treatment-related AEs leading to discontinuation, and treatment-related SAEs all occurred more commonly in subjects in the N1 + I3 arm than in the N3 + I1 arm: treatment related AEs 76.2% N3 + N1 versus 100% N1 + I3; treatment related grade 3-4 AEs 28.6% versus 60.9%, treatment related AEs leading to discontinuation 9.5% versus 26.1%.

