7.1 Dose Delays for Nivolumab with or without Ipilimumab

Nivolumab with or without ipilimumab administration should be delayed for the following:

- Any Grade ≥ 2 non-skin, drug-related adverse event, with the following exceptions:
 - Grade 2 drug-related fatigue or laboratory abnormalities do not require a treatment delay
- Any Grade 3 skin, drug-related adverse event
- Any Grade 3 drug-related laboratory abnormality, with the following exceptions for AST, ALT, or total bilirubin:
 - If a subject has a baseline AST, ALT, or total bilirubin that is within normal limits, delay dosing for drug-related Grade ≥ 2 toxicity
 - If a subject has baseline AST, ALT, or total bilirubin within the Grade 1 toxicity range, delay dosing for drug-related Grade ≥ 3 toxicity
- Grade 3 amylase or lipase abnormalities that are not associated with symptoms or clinical manifestations of pancreatitis do not require a dose delay. It is recommended to consult with the PI for Grade 3 amylase or lipase abnormalities.
- Any adverse event, laboratory abnormality, or intercurrent illness which, in the judgment of the investigator, warrants delaying the dose of study medication.

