
7.3 Criteria to Discontinue Treatment with Nivolumab with or without Ipilimumab

Treatment with nivolumab with or without ipilimumab should be permanently discontinued for any of the following:

- Any Grade 2 drug-related uveitis or eye pain or blurred vision that does not respond to topical therapy and does not improve to Grade 1 severity within the re-treatment period OR requires systemic treatment
- Any Grade 3 non-skin, drug-related adverse event lasting $>$ 7 days, with the following exceptions for drug-related laboratory abnormalities, uveitis, pneumonitis, bronchospasm, diarrhea, colitis, neurologic toxicity, hypersensitivity reactions, and infusion reactions:

- Grade 3 drug-related uveitis, pneumonitis, bronchospasm, diarrhea, colitis, neurologic toxicity, hypersensitivity reaction, or infusion reaction of any duration requires discontinuation
- Grade 3 drug-related laboratory abnormalities do not require treatment discontinuation except:
 - Grade 3 drug-related thrombocytopenia > 7 days or associated with bleeding requires discontinuation
 - Any drug-related liver function test (LFT) abnormality that meets the following criteria require discontinuation:
 - * AST or ALT > 8 x ULN
 - * Total bilirubin > 5 x ULN
 - * Concurrent AST or ALT > 3 x ULN and total bilirubin > 2 x ULN
- Any Grade 4 drug-related adverse event or laboratory abnormality, except for the following events which do not require discontinuation:
 - Grade 4 amylase or lipase abnormalities that are not associated with symptoms or clinical manifestations of pancreatitis. It is recommended to consult with the PI for Grade 4 amylase or lipase abnormalities.
 - Isolated Grade 4 electrolyte imbalances/abnormalities that are not associated with clinical sequelae and are corrected with supplementation/appropriate management within 72 hours of their onset
- Any dosing interruption lasting > 6 weeks unless the sponsor-investigator is consulted and agrees with the rationale for resuming therapy after a delay > 6 weeks. Note that tumor assessments should continue as per protocol even if dosing is interrupted.
- Any adverse event, laboratory abnormality, or intercurrent illness which, in the judgment of the site investigator, presents a substantial clinical risk to the subject with continued nivolumab with or without ipilimumab dosing.

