12.6 Routine Adverse Event Reporting

All Adverse Events **must** be reported in routine study data submissions to the Overall PI on the toxicity case report forms. **AEs reported through expedited processes (e.g., reported to the IRB, FDA, etc.) must also be reported in routine study data submissions.**

Abnormal laboratory values or diagnostic test results constitute AEs only if they induce clinical signs or symptoms or require treatment or further diagnostic tests.

Wherever possible, timely confirmation of initial liver-related laboratory abnormalities should occur prior to the reporting of a potential drug-induced liver injury (DILI) event. All occurrences of potential DILIs, meeting the defined criteria, must be reported as SAEs.

Potential drug induced liver injury is defined as:

- 1) AT (ALT or AST) elevation > 3 times upper limit of normal (ULN)

AND

- 2) Total bilirubin > 2 times ULN, without initial findings of cholestasis (elevated serum alkaline phosphatase)

AND

- 3) No other immediately apparent possible causes of AT elevation and hyperbilirubinemia, including, but not limited to, viral hepatitis, pre-existing chronic or acute liver disease, or the administration of other drug(s) known to be hepatotoxic.

Hospitalization for elective surgery or routine clinical procedures that are not the result of an AE (e.g., surgical insertion of central line) should not be recorded as an AE.

Disease progression should not be recorded as an AE, unless it is attributable to the study regimen by the site investigator.

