13.7.2 Secondary Analysis

PFS and OS: The progression-free survival (PFS), and overall survival (OS) will each be summarized using the product-limit method of Kaplan-Meier. Median times for each endpoint will be presented with two-sided 90% confidence intervals estimated using log(-log(survival)) methodology. Kaplan-Meier estimates of PFS at 6 or 12 months may also be presented with two-sided 90% confidence intervals.

Salvage Therapy-Free Interval: The proportion of subjects re-start nivolumab since nivolumab discontinuation (arm A) during 1-year will be estimated with two-sided 90% confidence intervals. In addition, the reasons for re-starting nivolumab (Arm A) will be tabulated.

Subset analysis of study endpoints will be explored according to IMDC* risk group (favorable, intermediate, versus poor risk); prior systemic treatment for RCC (yes versus no); first line versus second line targeted therapy; histology (clear cell versus non-clear cell RCC subtypes; sarcomatoid components present versus absent)

*IMDC risk factors include ECOG < 1, time from original diagnosis to treatment less than one year, hemoglobin less than the lower limit of normal, and serum calcium, neutrophil count, or platelet count greater than the upper limit of normal

Immune Related Objective Response Rate: The proportion of subjects with immune ORR will be presented with two-sided 90% confidence interval estimated using exact binomial methods.

Safety and Tolerability: All adverse events recorded during the trial will be summarized for the safety population. The incidence of events that are new or worsening from the time of first dose of treatment will be summarized according to system organ class and/or preferred term, severity (based on CTCAE version 4), type of adverse event, and relation to study treatment.

The worst grade will be used if any toxicity event is reported multiple times on the same participant. All adverse events resulting in discontinuation, and/or dosing interruption, and/or treatment delay will also be summarized.

Given the potential multiple treatment sequences, the incidence of events (grade 3+) will be summarized according to treatment arms as well as the type of therapies they are on at the time of events.

Deaths reportable as SAEs and non-fatal serious adverse events will be listed by patient and tabulated by primary system organ class, and type of adverse event.

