3.9 Safety Assessments and Toxicity Monitoring

The study teams at all participating institutions are responsible for protecting the safety, rights and well-being of study participants. Recording and reporting of adverse events that occur during the course of a study help ensure the continuing safety of study participants.

All participants receiving investigational agents and/or other protocol mandated treatment will be evaluated for safety. The safety parameters include all laboratory tests and hematological abnormalities, physical examination findings, and spontaneous reports of adverse events reported by participants. All toxicities encountered during the study will be evaluated according to the NCI criteria specified in the protocol. Life-threatening toxicities must be reported to the DF/HCC Sponsor within 1 business days of becoming aware of the event.

Additional safety assessments and toxicity monitoring is outlined in the protocol.

Guidelines for Reporting Serious Adverse Events

Guidelines for reporting Adverse Events (AEs) and Serious Adverse Events (SAEs) are detailed in protocol Section 12.

Participating Institutions must report the SAEs to the Coordinating Center according to the protocol.

The Coordinating Center will maintain documentation of all Participating Institution Adverse Event reports and be responsible for communicating to all participating investigators, any observations reportable under the protocol requirements. Participating Institutions will review and submit to their IRB according to their institutional policies and procedures

Guidelines for Processing IND Safety Reports

The DF/HCC Sponsor will review all IND Safety Reports and ensure that all IND Safety Reports are distributed to the Participating Institutions. Participating Institutions will review and submit to their IRB according to their institutional policies and procedures.

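### A laboratory value that delays or stops dosing under Section 7 need not be an AE under 12.6, so the AE-based safety summaries may be undercounted

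*Combined protocol and SAP*

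**What the plan says.** Section 12.6 (Routine Adverse Event Reporting) states that abnormal laboratory or diagnostic results "constitute AEs only if they induce clinical signs or symptoms or require treatment or further diagnostic tests". It also makes every potential drug-induced liver injury (DILI), defined by laboratory limits and exclusions, reportable as an SAE.

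Section 7.1 lists among the reasons to delay dosing "Any Grade 3 drug-related laboratory abnormality, with the following exceptions for AST, ALT, or total bilirubin". One of those liver-test rules reads "If a subject has a baseline AST, ALT, or total bilirubin that is within normal limits, delay dosing for drug-related Grade" 2 or higher. Section 7.3 adds permanent stops: "Any drug-related liver function test (LFT) abnormality that meets the following criteria require discontinuation", followed by multiples of the upper limit of normal (ULN). It also stops treatment for Grade 3 thrombocytopenia that is prolonged or accompanied by bleeding, and for Grade 4 laboratory abnormalities apart from two exemptions.

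Section 13.7.2 plans the incidence of Grade 3+ events by arm and by therapy at the time of the event. It then says: "All adverse events resulting in discontinuation, and/or dosing interruption, and/or treatment delay will also be summarized". Section 13 contains no table of laboratory results by grade.

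**The concern.** The rule that decides what becomes an AE and the rules that decide when dosing is delayed or stopped use different criteria. Section 7 mostly acts on a grade or a multiple of ULN. Section 12.6 asks about symptoms, treatment and further testing. The safety tables are filled through 12.6, so a laboratory value that triggers a Section 7 action can be missing from the table meant to show such actions, and from the Grade 3+ table.

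Safety in both arms is a secondary objective (3.1.2). Section 2.4 shows that laboratory events were prominent in the cited phase I combination study, where the most common "drug-related grade 3-4 events were lipase increased (21%), ALT increased (14%), AST increased (7"%). Under 13.5 the monitoring committee reviews relevant adverse events, and under 14.2 laboratory values reach it on request, so routine oversight largely passes through the same filter.

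**Working it through.** No design figure is involved, so the check sets the passages side by side. For each laboratory trigger the questions are: does Section 7 require symptoms, does 12.6 make it an AE, and which 13.7.2 summary is exposed?

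| Laboratory finding (drug-related) | Section 7 action | Symptoms required? | AE under 12.6? | Summary exposed |
|---|---|---|---|---|
| Grade 3 value outside the liver-test and amylase/lipase rules | Delay (7.1) | No | Only if symptomatic, treated or tested further | Delay and Grade 3+ |
| AST, ALT or bilirubin, normal baseline, Grade 2 or higher | Delay (7.1) | No | Same | Delay; also Grade 3+ from Grade 3 |
| AST, ALT or bilirubin, Grade 1 baseline, Grade 3 or higher | Delay (7.1) | No | Same | Delay and Grade 3+ |
| AST or ALT > 8 x ULN; bilirubin > 5 x ULN; or AST/ALT > 3 x ULN with bilirubin > 2 x ULN | Stop (7.3) | No | Often, through work-up or steroids; the combined limit may also be DILI | Discontinuation and Grade 3+, where not caught |
| Grade 3 thrombocytopenia > 7 days or with bleeding | Stop (7.3) | No for the duration limb | Bleeding: yes. Duration: turns on whether repeat counts qualify | Discontinuation and Grade 3+ |
| Other Grade 4 values | Stop (7.3) | No | Only if symptomatic, treated or tested further | Discontinuation and Grade 3+ |
| Grade 3 or 4 amylase/lipase without pancreatitis | None | Exempt | Only if treated or tested further | Grade 3+ only |
| Isolated Grade 4 electrolyte abnormality without clinical sequelae, corrected within 72 hours | No stop | Exempt from stopping | Correction by supplementation is treatment, so normally yes | Little or none |

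Three points follow.

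1. In the first six rows Section 7 can act on a number alone. The action does not itself make the finding an AE.
2. The phrase on further testing in 12.6 carries much of the weight. Resuming after a delay requires resolution to Grade 1 or baseline, with listed exceptions (7.2), which in practice means another blood test. The protocol does not say whether that qualifies. CBC and chemistry are already scheduled visit by visit in Section 8, so one site could call the repeat further testing and another could call it routine.
3. DILI reporting closes only part of the gap. It needs AST or ALT > 3 x ULN together with bilirubin > 2 x ULN, no initial cholestasis and no other apparent cause. An isolated AST or ALT > 8 x ULN stops treatment under 7.3 but is not DILI.

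Can the size be taken from the documents? For the nivolumab 3 mg/kg + ipilimumab 1 mg/kg column of Table 5 (N = 21), the laboratory terms in the block of events seen in at least 20% of subjects have these Grade 3-4 counts: ALT 0, AST 0, lipase 3. Asymptomatic lipase is exempt from Section 7 action, and lipase is not in the panels listed in the Section 8 footnotes. Table 5 does not say which events were asymptomatic, untreated or not followed up. It therefore gives no estimate of how many Section 7 actions would lack an AE.

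**The case against.** The strongest reply is that most Section 7 triggers will meet 12.6 in practice. A liver value high enough to stop treatment falls under the hepatic algorithm in Appendix C, which calls for ruling out other causes, suggests imaging and gives a steroid dose for Grade 4 hepatitis. Delayed doses lead to repeat tests. Thrombocytopenia lasting more than 7 days cannot be established without repeat counts. Potential DILI is an SAE. Section 6.5 also requires the reason and date of removal from therapy on the case report form, so permanent stops leave a trace.

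Much of this stands, and it is why the conclusion is that counts may be low, not that they will be. It does not close the gap. Appendix C is advisory, and departures from it are not treated as deviations. The status of a repeat blood test is left to each site. A value that ends treatment needs no repeat test to satisfy the resume rule. Section 6.5 covers removal from therapy, not delays, and its record does not feed the AE tables.

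A reader might also infer that Appendix D, 3.9 contradicts 12.6, because it says "The safety parameters include all laboratory tests and hematological abnormalities". It does not. It lists what is evaluated for safety, whereas 12.6 decides what is labelled an AE, and 3.9 itself refers to Section 12 for AE reporting guidelines.

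**Conclusion.** The mismatch is real and worth correcting. As written, a laboratory-driven delay or stop can be absent from the Grade 3+ and delay/discontinuation summaries, and ascertainment may vary between sites. Whether an undercount occurs depends on how sites read 12.6 and how often affected patients are treated or worked up. The documents give neither, so the size is unknown. Primary endpoints, the Arm A and Arm B decision rules and the sample size do not depend on it.

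Two stronger readings are tempting and are not supported:

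- **The drug-related Grade 3-4 rate would be halved.** Table 5 gives 6/21 = 28.6% for the regimen used here. Removing all three lipase cases gives (6 - 3)/21 = 3/21 = 14.3%. This assumes that each was the patient's only Grade 3-4 event and would fail 12.6. The documents show neither, and if none of the three is lost the rate stays at 28.6%. The example also cannot illustrate missing delays or stops, because 7.1 and 7.3 exempt asymptomatic lipase.
- **The trial will look safer than the phase I study through its definition alone.** The documents do not give that study's rule for laboratory AEs, which may have been the same, and Section 13 plans no safety comparison with it.

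**What to change.** Make two reporting changes. Neither alters a rule on delaying, stopping or resuming treatment.

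1. In 12.6, add that a laboratory abnormality is also recorded as an AE when it leads to dose delay, interruption or discontinuation under Section 7. This covers the Grade 2 liver-test delays and makes the status of a repeat test immaterial for those cases. State in the same place whether a repeat laboratory test counts as a further diagnostic test, for cases where dosing is unaffected.
2. In 13.7.2, add a table of worst CTCAE grade per patient, by arm and by therapy at the time, for the scheduled CBC and chemistry results. Grade 3+ values are then reported whether or not they are labelled AEs. Amylase and lipase are outside those panels and would still appear only as AEs.

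The cost is a sentence or two in 12.6, matching case report form guidance and one further table. Section 15.2 allows some standard-of-care data to remain in source documents, so confirm that the laboratory results are entered in the trial database before relying on them for the table. The downside is somewhat more AE entries and a slightly higher reported AE rate.

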12.7 Pregnancy

If, following initiation of the investigational product, it is subsequently discovered that a study participant is pregnant or may have been pregnant at the time of investigational product exposure, including during at least 5 half-lives after product administration, the investigational product will be permanently discontinued in an appropriate manner (eg, dose tapering if necessary for participant).

The investigator must immediately notify [REDACTED] of this event via the Pregnancy Surveillance Form in accordance with SAE reporting procedures.

Protocol-required procedures for study discontinuation and follow-up must be performed on the participant.

Follow-up information regarding the course of the pregnancy, including perinatal and neonatal outcome and, where applicable, offspring information must be reported on the Pregnancy Surveillance Form (provided upon request from BMS).

Any pregnancy that occurs in a female partner of a male study participant should be reported to BMS. Information on this pregnancy will be collected on the Pregnancy Surveillance Form. In order for Sponsor or designee to collect any pregnancy surveillance information from the female partner, the female partner must sign an informed consent form for disclosure of this information.

13. STATISTICAL METHODS

13.1 Study Design

The study uses a single arm phase II design. Originally the study planned to enroll a total of 58 subjects into the two treatment Arms A and B. The design details are stated in Section 2.7.

Single Cell Sequencing Cohort: The study was amended to enroll an additional cohort of 25 patients to allow for single cell molecular transcriptomic assessment. These additional 25 patients will undergo the following biopsy schedule:

Arm A:

Mandatory biopsy at baseline

Optional biopsy at time of response following discontinuation of nivolumab

Mandatory biopsy at final treatment discontinuation/off study

Arm B:

Mandatory biopsy at baseline

Mandatory biopsy at final treatment discontinuation/off study

The cohort addition increases the overall enrollment to 83 subjects in the trial.

No stratification factors are used in enrolling subjects.

13.2 Endpoints

13.2.1 Definition of Primary Endpoint

- The number and proportion of subjects remaining on PR or CR at 1 year since nivolumab discontinuation (Arm A) and the number and proportion of subjects achieving PR or CR upon the addition of ipilimumab to nivolumab (Arm B).
- The response status of PR or CR will be assessed according to RECIST criteria v1.1.

13.2.2 Definition of Secondary Endpoints

- Progression-free survival (PFS): defined as the time from nivolumab discontinuation (Arm A) or from ipilimumab initiation (Arm B) until documented progression by

RESIST criteria or death from any cause, censored at date last known progression-free for those who are alive and have not progressed.

- Overall Survival (OS): defined as the time from nivolumab discontinuation (Arm A) or from ipilimumab initiation (Arm B) until death from any cause, censored at date last known alive or at the time of last assessment of follow-up.
- Salvage therapy-free interval: defined as time from nivolumab discontinuation (arm A) to the receipt of re-starting nivolumab.
- Immune related objective response rate defined according to immune-related Responses Criteria (irRC) and detailed in section 10.5.
- Safety and tolerability according to NCI CTCAE v4.

13.2.3 Definition of Correlative Endpoints

Marker assessments:

- Tumor expression for PD-L1 expression in baseline (prior to primary nivolumab) biopsy tissue, and progression biopsy specimens will be analyzed in all evaluable samples.
- WES, RNAseq, and IHC assessment of immunologic parameters including Tumor-infiltrating lymphocytes (TILs), T cell markers (CD4, CD8, FoxP3, LAG3), cytokines/chemokines (IFN, TNF), immune regulation (PD-L1, PD-L2, CTLA-4) will be evaluated in fresh tumor specimens obtained prior to initial nivolumab in order to assess the mechanisms of responses to nivolumab, with the focus on subjects with a durable response (confirmed PR/CR) to the nivolumab assessed during the 1st year since the discontinuation of the primary nivolumab start (Arm A)
- Mechanisms of intrinsic and acquired resistance to nivolumab (alone, Arm A) and with ipilimumab (Arm B) in fresh tumor specimens obtained at time of radiographic progression by WES, RNAseq, and IHC assessment of immunologic parameters including T cell subset markers (CD4, CD8, FoxP3, LAG3), cytokines/chemokines (IFN, TNF), immune regulation (PD-L1, PD-L2, CTLA-4), and TILs
- cfDNA and CTC evaluated as baseline, on treatment, and at progression.
- Single cell molecular profile according to baseline and metastasis biopsy specimens

